## 1 SYNOPSIS

Title	Drug Utilization Study in Patients Receiving Ozurdex™ (Dexamethasone Intravitreal Implant) 0.7 mg Injections for Visual Impairment due to Diabetic Macular Edema (DME) [REDACTED] [REDACTED]
Protocol number	CMO-MA-EYE-0564
Clinical Trials.gov Registration Number	Not yet registered
Planned study dates	Data abstraction is planned to be conducted between third and fourth quarters of 2018.
Objectives	
Primary objective The primary objective of this study is to assess reinjection interval of Ozurdex implants in patients with DME in real-world in Germany and Switzerland.
 
Secondary objectives The secondary objectives of this study are:
 
 
• To assess relationship between reinjection intervals and effectiveness
 
• To describe the reasons for reinjection
 
• To assess drug effectiveness in patients who are naïve of any anti-vascular endothelial growth factor (VEGF) treatment
 
• To present those adverse events of special interest (AESIs) that may be potentially related to Ozurdex reinjection
 

Study Design	This is a retrospective, non-interventional, observational, multi-center, drug utilization study to be conducted in adult patients with visual impairment due to DME treated with Ozurdex implants in Germany and Switzerland. The design is based on secondary use of data already collected in medical records for routine clinical care purpose.
Rationale	Drug utilization in real world may not always reflect what has been described in clinical trials. Thus, there is a need for data derived from more heterogeneous patient populations in real-world healthcare settings, such as in observational cohorts, in order to help physicians gain a better understanding of the use of Ozurdex. This retrospective study was designed to assess the reinjection interval of Ozurdex in routine clinical practice in Germany and Switzerland and its relationship with effectiveness and safety of the drug. Study outcomes will enhance knowledge of this treatment option.

Duration of study	For each patient, data abstraction will cover at least one year of follow-up from date of first Ozurdex implant injection up to 1 September 2018. Overall data will be abstracted from 1 January 2015 until 1 September 2018.

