In the MEADs trials, the most commonly reported AEs following treatment with Ozurdex are those frequently observed with ophthalmic steroid treatment or intravitreal injections: cataract formation, elevated intra-ocular pressure (IOP), and conjunctival or vitreal hemorrhage. In these trials, cataract-related AEs were observed in 67.9% of patients with a phakic eye at baseline compared to 20.4% of patients in the sham group. The incidence of cataract-related AEs increased after the first year after Ozurdex injection. Approximately one-third of patients with Ozurdex implant had a clinically significant increase in IOP requiring treatment during the study. Vitreous hemorrhage considered possibly related to treatment was reported in 3.5% of patients with Ozurdex implant compared to 0.0% in the sham group. Less frequently reported but more serious adverse drug reactions include endophthalmitis, necrotizing retinitis, retinal detachment and retinal tear. With the exception of headache and migraine, no systemic adverse drug reactions were identified with the use of Ozurdex. Finally, several adverse drug reactions, such as conjunctival hemorrhage, visual acuity reduced, vitreous detachment, vitreous floaters, vitreous opacities, eye pain, photopsia, conjunctival edema, conjunctival hyperemia, endophthalmitis, retinal detachment, retinal tear, hypotony of the eye, anterior chamber inflammation, anterior chamber cells/flare, abnormal sensation in eye, scleral hyperemia, device dislocation, and complication of device insertion, have been identified in Ozurdex SmPC as related to the intravitreal injection procedure, i.e. the frequency of these AEs is proportional to the number of treatments given.

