#### 8.2.1 Inclusion Criteria

A patient must meet **all** of the following criteria to be eligible for participation in the study.

1. Patient received at least two Ozurdex implants in the study eye to treat visual impairment due to DME
2. Male or female patient aged  $\geq 18$  years at time of first Ozurdex implant injection
3. First Ozurdex implant injection occurred after 1 January 2015
4. Patient was followed-up at the site for at least 12 months after the first Ozurdex implant in the study eye

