### Sites and study population

Site selection will aim to recruit qualified ophthalmologists experienced in intravitreal injections who are most likely to treat patients with DME with Ozurdex. A sample of ophthalmologists working in experienced medical retinal centers treating DME patients will thereby be selected.

From a public health and market access perspective, the present study population constitutes a broader real-world patient population than that reflected in clinical trials. The present study design cannot make any conclusions on causal relationships, but can rather explore real-world Ozurdex drug utilization patterns, effectiveness and safety. It is expected that the results from this study may be generalizable to the overall population presenting with DME and treated with Ozurdex in Germany and Switzerland.

Patients may contribute at most one eye into the study. If both eyes meet the inclusion and exclusion criteria, the eye that received the most Ozurdex injections will be chosen as the study eye.

Inclusion criteria are:

1. Patient received at least two Ozurdex implants in the study eye to treat visual impairment due to DME

2. Male or female patient aged  $\geq 18$  years at time of first Ozurdex implant injection in the study eye
3. First Ozurdex implant injection in the study eye occurred after 1 January 2015
4. Patient was followed-up at the site for at least 12 months after the first Ozurdex implant injection in the study eye

Exclusion criterion is:

1. Patient received Ozurdex implants in the study eye as part or during a clinical study

[REDACTED]

[REDACTED]

[REDACTED]

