### 15.2.4 Fourth Secondary Objective

The secondary objective '*To present those AESIs that may be potentially related to Ozurdex reinjection*' will be assessed by the presence of the following AESIs:

- Cataract or lens opacities
- Glaucoma
- Hypotony
- Implant dislocation
- Infection vs. Non-infection related ocular inflammation
- Intraocular hypertension
- Mechanical failure of device and implant misplacement
- Ocular bleeding or hemorrhage
- Retinal detachment (tear or hole)
- Significant vitreous loss
- Vitreous detachment

These AESIs will be identified from eCRF section '*Adverse events*' (AE/F20 form) in which they are pre-listed.

All AESIs that began on or after the date of the first Ozurdex injection in the study eye will be considered for analysis. The analysis will be performed:

- considering all AESIs, AESIs that occur in the study eye, and AESIs that occur in the contralateral eye.
- cumulatively considering all AESIs and broken down by the number of injections, i.e. considering AESIs that occur after the first Ozurdex injection at baseline, AESIs that occur after the first Ozurdex reinjection, AESIs that occur after the second Ozurdex reinjection, etc. AESIs that occur on the same day of an Ozurdex injection will be considered as occurring after the injection.

AESIs will be summarized using descriptive statistics for the following parameters:

- Number and percentage (with 95% CI) of patients who experienced at least one AESI.

[REDACTED]

[REDACTED]

[REDACTED]

[REDACTED]

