### Follow-up period

The period starting the day after the day of the first Ozurdex injection in the study eye is the follow-up period (= post-baseline period). End of follow-up occurs at the last study visit or first receipt of concomitant treatment with anti-VEGF and/or corticosteroids, whichever comes first.

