**Table 21-1 Definition of years after the first Ozurdex injection in the Study eye**

Year # [a]	Year definition [b]
Year 1	Days [2, 365]
Year 2	Days [366, 731]
Year 3	Days [732, 1096]

---

- [a] As per protocol all patients will have at least 1 complete year of follow-up at the site and the maximum number of complete years will be 3. The 1st Ozurdex injection should occur after 1 January 2015 and data will be collected up to 1 September 2018.
- [b] Relative to the date of the first Ozurdex injection in the study eye. Day 1 = the date of the first Ozurdex injection in the study eye. There is no Day 0.

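### The visible AESI percentage pools 12 to 44 months of follow-up, so it is not a risk at any stated time and cannot be compared with 3-year trial figures

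*SAP*

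**What the plan says.** SAP 15.2.4 sets the time frame for safety events: "All AESIs that began on or after the date of the first Ozurdex injection in the study eye will be considered for analysis". It gives no upper time limit. The visible summary measure is the "Number and percentage (with 95% CI) of patients who experienced at least one AESI", shown cumulatively and by injection number. Several lines after that bullet are redacted. SAP 16.0 refers back to 15.2.4 for the whole safety analysis.

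The lower limit of follow-up comes from Protocol 8.2.1: "Patient was followed-up at the site for at least 12 months after the first Ozurdex implant in the study eye". SAP 4.0 repeats it. The upper limit comes from the Protocol Synopsis: "Overall data will be abstracted from 1 January 2015 until 1 September 2018". SAP Table 21-1 accordingly notes that "the maximum number of complete years will be 3".

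SAP 21.2 also has a general stopping rule: "End of follow-up occurs at the last study visit or first receipt of concomitant treatment with anti-VEGF and/or corticosteroids, whichever comes first". SAP 15.2.4 does not say whether this rule applies to AESIs.

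On the time pattern of harm, Protocol 5.1 says of the phase III trials: "The incidence of cataract-related AEs increased after the first year after Ozurdex injection". It gives 67.9% for cataract-related events in patients with a phakic eye at baseline, from trials lasting 3 years. Protocol 7.3.3 and SAP 7.0 foresee comparing safety events with the literature through subgroups.

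**The concern.** A crude percentage answers a clear question only if everyone is watched for about the same time. Here an eye seen for 12 months without an event counts the same as an eye seen event-free for 44 months. By the protocol's own account, cataract risk rises in the period after month 12, where follow-up is no longer guaranteed. The binomial interval around the percentage does not reflect this, because it treats every patient as equally observed.

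The SAP deals with the same problem elsewhere. For the primary objective, SAP 15.1 limits the Year 2 and Year 3 denominators to patients with that complete year. No such protection is visible for AESIs. The split by injection number does not supply it, because patients with the same number of injections can have been observed for different times.

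What is at stake is how the safety result is read. If it is set beside published figures, a difference could reflect follow-up length or the share of phakic eyes rather than any difference in risk.

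**Working it through.** **Follow-up range.** From 1 January 2015 to 1 September 2018 is 1339 days. With the SAP convention of 30.4375 days per month, 1339 / 30.4375 = 43.99 months, and 1339 / 365.25 = 3.67 years. This reproduces the SAP's maximum of 3 complete years. From 1 September 2017, the last first-implant date in Protocol 9.2, to 1 September 2018 is 365 days, or 11.99 months. The range is therefore 12 to 44 months. If the SAP 21.2 stopping rule applies to AESIs, some eyes fall below 12.

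**Effect on a crude percentage.** The documents give no yearly rates and no distribution of follow-up. The following is an illustration on assumed inputs:

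- 67.9% is taken as the 36-month risk in phakic eyes.
- The hazard is h per month up to month 12 and r × h after it. r = 1 is a constant hazard; r above 1 mimics the rise that the protocol reports.
- Follow-up is uniform over the interval shown.

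The total hazard at 36 months is −ln(1 − 0.679) = 1.1363, so h = 1.1363 / (12 + 24r). For r = 1, h = 1.1363 / 36 = 0.03156. The risk by month t is F(t) = 1 − exp(−ht), and the crude percentage over [a, b] is the mean of F:

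1 − [exp(−ha) − exp(−hb)] / [h(b − a)]

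For 12-44 months: exp(−12h) = 0.6847 and exp(−44h) = 0.2494, so 1 − 0.4353 / 1.0101 = 0.569.

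| Follow-up | r = 1 | r = 2 | r = 3 | r = 5 |
|---|---|---|---|---|
| All at 12 months | 31.5% | 20.3% | 15.0% | 9.8% |
| Uniform 12-28 | 46.2% | 40.3% | 37.5% | 34.8% |
| Uniform 12-44 | 56.9% | 53.8% | 52.4% | 51.0% |
| Uniform 28-44 | 67.6% | 67.4% | 67.3% | 67.3% |
| Uniform 36-44 | 71.6% | 72.3% | 72.6% | 72.8% |
| All at 44 months | 75.1% | 76.3% | 76.8% | 77.3% |

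Every cell has the same 67.9% risk at 36 months. Against that figure, the crude percentage is 11 to 17 points lower for 12-44 months, within 1 point for 28-44, and 4 to 5 points higher for 36-44. It equals 67.9% when follow-up is uniform from about 28.6-28.8 months to 44.

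**Effect of the denominator for cataract.** Suppose all eyes formed the denominator and only phakic eyes could have the event. A risk of 67.9% in phakic eyes would then appear as 0.25 × 67.9 = 17.0%, 0.50 × 67.9 = 34.0% or 0.75 × 67.9 = 50.9%, for assumed phakic shares of 25%, 50% and 75%.

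**What the visible methods cover.** SAP 21.1 describes means, percentages and their intervals. SAP 21.3 is presented as defining every derived variable. For AESIs it has event duration and time since the last implant. It has neither time from first implant to first AESI nor person-time.

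**The case against.** The strongest objection concerns direction. A reader might infer that the AESI result will read too low against the 3-year trials and so flatter the drug. The documents do not support that. Protocol 9.2 has sites start with the patients treated closest to 1 January 2015, which favours long follow-up, and follow-up can exceed 36 months. On the other hand, only 12 months at the site are required, so an early starter may still have a short record. As the table shows, the crude figure can fall below, match or exceed 67.9%. This part of the objection stands.

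The second objection is redaction. The quoted bullet covers any AESI; no cataract-specific percentage is visible in SAP 15.2.4. Such a figure, or a time-based summary, could be in the hidden lines. That also stands, so nothing here says that these outputs are absent. It does not change the visible percentage.

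Third, SAP 7.0 names neither the 67.9% nor the trials it comes from; it speaks of the literature in general, in a passage on background risk. A specific side-by-side comparison should not be attributed to it. However, Protocol 5.1 supplies that figure for cataract, and any comparison with the literature needs matched follow-up.

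Fourth, the plan already reports study duration (SAP 8.0), changes in lens status (SAP 12.1) and time to first surgical procedure (SAP 13.4), and the objective is only to present AESIs. These help a reader judge follow-up, but they do not turn the percentage into a risk at a known time. The modest objective lowers the urgency and does not remove the point.

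**Conclusion.** The point holds in limited form. The visible AESI percentage mixes follow-up of 12 to 44 months and is not a risk at any stated time. It is not comparable with 3-year trial figures, in a direction that the documents leave open. For cataract there is a second mismatch: the cited figure is for phakic eyes, and no phakic-only AESI denominator is visible.

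With a constant hazard, the same underlying risk gives about 46% to 72% across the four uniform follow-up patterns. These sizes rest on assumptions: 67.9% as a true 36-month risk, the hazard shape, the follow-up distributions and the phakic shares. Only the 12-to-44-month range comes straight from the documents. This is a worthwhile and cheap improvement to a descriptive secondary objective that carries the study's whole safety analysis. The primary result is not affected.

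**What to change.** In SAP 15.2.4:

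- Add the cumulative incidence of first AESI in the study eye, any and by type, at 12, 24 and 36 months from the first study-eye implant. Kaplan-Meier estimates with 95% CI and numbers at risk would serve.
- Restrict the cataract estimate to eyes phakic at baseline.
- State the censoring date, and whether the SAP 21.2 rule on concomitant anti-VEGF or corticosteroid treatment ends follow-up for AESIs.
- Compare with the literature only at a matching time point and lens status.
- Keep the crude percentage as a descriptive line, shown with the distribution of follow-up.

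The cost is SAP wording, one derived variable in SAP 21.3 and a standard procedure. AESI onset date, first implant date, last visit date and baseline lens status are already used in the SAP, so no new data are needed. The downside is that the 36-month estimate may be imprecise, and the method assumes that leaving follow-up is unrelated to the event.

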## **16.0 SAFETY ANALYSES**

Safety analysis is covered by the analysis of the secondary objective '*To present those AESIs that may be potentially related to Ozurdex reinjection*' (see Section 15.2.4).

**17.0 OFF-LABEL USE OF OZURDEX**

Off-label uses of Ozurdex will be identified from eCRF section '*Adverse events*' (AE/F20 form) and will be summarized by: number and percentage of patients with at least one off-label use of Ozurdex, and reason that caused Ozurdex use to be off-label (free text will be reported).

**18.0                    INTERIM ANALYSIS**

No interim analysis is planned for this study.

## **19.0 DETERMINATION OF SAMPLE SIZE**

The study aims to select 150 patients. As study primary objective is to assess reinjection interval of Ozurdex implant in real-world, sample size calculations were performed to evaluate the precision around the mean of the reinjection interval.

Few data were published on the reinjection interval in patients diagnosed with DME in real-world. Matropasqua et al. reported a mean  $\pm$  standard deviation (SD) of  $6.7 \pm 2.3$  months in 27 Italian patients. Querques et al. reported a mean of 4.9 and 4.7 months from respectively 570 French patients of a pharmacist database and 114 patients from the French Social Security database (no standard deviations were available). The same study also reported a mean ( $\pm$ SD) of  $4.8 \pm 1.8$  months between reinjections based on data from 111 French ophthalmologists who completed a survey about their practice.

The precision of the 95% CI of the mean ( $\omega$ , half of the width of the CI) is determined using the following formula:

$$\omega = \frac{1.96 \times SD}{\sqrt{n}}, \text{ where SD is the standard deviation and } n \text{ is the sample size.}$$

Table 18-1 shows the precision and 95% CI of the mean considering a SD ranging from 1.5 to 3.0 and a sample size of 150 patients.

**Table 18-1 Precision ( $\omega$ ) and 95% CI of the mean considering a standard deviation ranging from 1.5 to 3.0, a mean ranging from 4.7 to 6.7 and a sample size of 150 patients**

SD	Mean (months)				
	$\omega$	4.7	5.5	6.0	6.7
1.5	0.2	4.5-4.9	5.3-5.7	5.8-6.2	6.5-6.9
2.0	0.3	4.4-5.0	5.2-5.8	5.7-6.3	6.4-7.0
2.5	0.4	4.3-5.1	5.1-5.9	5.6-6.4	6.3-7.1
3.0	0.5	4.2-5.2	5.0-6.0	5.5-6.5	6.2-7.2

Considering SD of the mean reinjection interval ranging from 1.5 to 3 months, the selection of 150 patients will enable the description of a mean reinjection interval with precision ranging from 0.2 to 0.5 months, i.e. from 6 to 15 days (worst case).

For example, for a mean interval between two Ozurdex injections of 6.0 months, the 95% CI of the mean would be 6.0 [5.5-6.5] months in the worst case (i.e., 183 days [168-198],  $\omega = 15$  days).

A secondary objective of the study is to assess drug effectiveness in a subgroup of patients who are naïve of any anti-VEGF treatment. One of the outcomes of interest for this subgroup of patients will be the change in BCVA from the first injection to 7-12 weeks following each reinjection.

In 2015 Escobar-Barranco et al. reported a difference in visual acuity from baseline to 6 months (mean  $\pm$  SD) of  $11.5 \pm 4.6$  ETDRS letters in 36 treatment naïve patients whereas in 2018 Iglicki et al. reported a gain at 24 months (mean  $\pm$  SD) of  $11.3 \pm 10.0$  letters in 71 eyes of treatment naïve patients.

The precision and 95% CI of the mean have been calculated considering a mean gain of 11.5 letters, a standard deviation ranging from 4.5 to 10.0 and a sample size of 50 patients (Table 18-2).

**Table 18-2 Precision ( $\omega$ ) and 95% CI of the mean considering a mean gain of 11.5 letters, a standard deviation ranging from 4.5 to 10.0 and a sample size of 50 patients**

SD	$\omega$	95% CI
4.5	1.3	10.2-12.8
6.0	1.7	9.8-13.2
8.0	2.2	9.3-13.7
10.0	2.8	8.7-14.3

Considering SD ranging from 4.5 to 10.0, a subgroup of 50 patients who are treatment naïve will enable to describe a mean change in visual acuity with precision ranging from 1.3 to 2.8. For example, for a mean change in visual acuity of 11.5 letters, the 95% CI of the mean will be 11.5 [8.7-14.3] letters in the worst case. It has been considered as satisfactory for this secondary objective.

**20.0 STATISTICAL SOFTWARE**

Statistical analyses will be performed [REDACTED] [REDACTED]. Analysis datasets will be created from the raw EDC datasets to facilitate programming of Tables, Figures, and Listings (TFL). Proposed shells for TFLs will be provided in Microsoft Word format.

## **21.0 DATA HANDLING CONVENTIONS**

### **21.1 STATISTICAL RULES AND DATA FORMATS**

#### Continuous variables

Continuous (quantitative) variables will be described by the number of non-missing and missing observations, mean, SD, median, first and third quartiles and extreme values (minimum and maximum). The following rules will be applied:

- If the raw/derived variable is an integer, then mean, median, SD, first and third quartiles will be rounded to one decimal.
- If the raw/derived variable is a decimal number, then mean, median, SD, first and third quartiles will be reported using the same number of decimal places as the raw/derived data.
- Minimums and maximums will be reported with the same number of decimals with which the raw/derived variable is recorded/calculated.
- If the standard deviation is not computable, then it will be displayed as 'NA' (Not applicable).

#### Categorical variables

Categorical (qualitative) variables will be described by the observed and relative (%) frequency of each class, and number of non-missing and missing observations. Unless otherwise specified, missing data will not be included in the denominator for the calculation of percentages. If necessary, the denominator will be specified in a footnote to the tables for clarification. Multiple answers will also be specified, where applicable.

If 'Not in chart' or 'unknown' is a class of response, then it will be considered as missing for analysis.

Percentages will be rounded to one decimal place, except for the following specific cases:

- If the percentage is equal to 0, then a blank will be left instead of "0.0%"
- If the percentage is <0.1, then "<0.1%" will be used
- If the percentage is equal to 100, then "100%" will be used, i.e. no decimal place will be displayed
- If the percentage is >99.9, then ">99.9%" will be used.

### Confidence intervals

Confidence intervals for means and exact confidence intervals (Clopper-Pearson) for percentages will be calculated when appropriate and will be 2-sided at the 95% level.

### Figures

Figures will be performed when appropriate. In particular, the relationship between two continuous variables will be assessed using a scatter plot: one continuous variable will be plotted on the horizontal axis and the other continuous variable will be plotted on the vertical axis.

